The results of the proposed study will provide preliminary evidence on the feasibility and acceptability of a phone-delivered mindfulness training intervention for pregnant women at risk for hypertension disorders. Results will also provide evidence on the effectiveness of the intervention at reducing psychological symptoms of distress in pregnancy. Finally, results may provide preliminary evidence on the usefulness of such interventions on reducing rates of hypertension in at-risk women. We expect that these benefits will outweigh potential risks to participants.

Data and Safety Monitoring Plan:

[name] will have primary responsibility for monitoring all participants. Any adverse events, breaks of confidentiality, or any other data or safety issues that arise will be immediately brought to the attention of the RIH IRB. [name] will be responsible for completing an Adverse Events Form should an event occur. She will report Serious Adverse Events to the IRB within 24 hours of having received notice of the event. Adverse event reports will be reviewed annually with RIH IRB to ensure participant safety. In the

event that a study participant endorses suicidal ideation during an interview, the interviewer will complete a lethality assessment, will consult with the PI to formulate a course of action, and, with written permission, will consult with the participant's care provider. Appropriate intervention or follow-up care will be arranged with the treating clinician or, if hospitalization is required, through emergency services at Butler, The Miriam, or Rhode Island hospital.

Statistical Approach

Randomization. We will use a stratified randomization procedure to assign participants to mindfulness training vs. usual care based on medications for hypertension. The randomization scheme will be generated based on a permuted block randomization procedure with small random sized blocks. Randomization will be stratified by hypertension medications (yes/no).

Sample size considerations. The proposed sample size was estimated to have sufficient power to assess feasibility and acceptability, as well as to provide a reasonable sample with which to estimate effect sizes and confidence intervals for secondary outcomes. We propose to enroll 30 participants in a 1:1 ratio to mindfulness training and usual care. With a two-sided alpha-level of 0.05, we will have more than sufficient power (>80%) to detect acceptability differences in the small-medium range, $d=0.45/w=.2$.

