Specific Aim 1: To test feasibility and acceptability of phone-delivered mindfulness training for pregnant women with a history of hypertensive disorders of pregnancy. 30 pregnant women with a history of hypertensive disorders of pregnancy will be recruited and randomly assigned to MT (N=15) or to treatment as usual (N=15). Primary outcomes are feasibility and acceptability ($>75\%$ attend at least 4 sessions; > 20 on the client satisfaction questionnaire). We will explore preliminary effects (not powered for efficacy) of group differences in ambulatory blood pressure (average daytime, nighttime, and diurnal systolic, diastolic blood pressure, hyperbaric index, blood pressure variability, and dipping status). We will also examine rates of hypertensive disorder recurrence that will be fully tested in a future fully-powered RCT.

Specific Aim 2: Conduct a qualitative analysis of feasibility and acceptability of phone-delivered mindfulness training for pregnant women with a history of hypertensive disorders of pregnancy. Following the mindfulness intervention, we will conduct individual qualitative interviews to solicit feedback on participants' treatment satisfaction, motivation for

participation, barriers and challenges to participation, and appropriateness of the session content for hypertension in pregnancy. Information gained in the qualitative analysis will be used to improve feasibility and acceptability in the future fully-powered RCT.

Specific Aim 3: To examine differences in pathophysiological mechanisms of hypertensive disorders of pregnancy among women receiving mindfulness training vs. usual care. We hypothesize that pregnant women receiving mindfulness training will display reduced inflammation, improved uterine perfusion and fetal growth, and reduced blood pressure, and these mechanisms will in turn reduce risk for hypertensive disorder recurrence.

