Participants assigned to the MT intervention will receive 30-minute phone-delivered MT sessions once a week for 8 weeks. [name], a faculty member in the Brown Center for Mindfulness, a certified mindfulness instructor, and an expert in mind-body approaches for cardiovascular health, developed this intervention. The MT intervention is based upon the curriculum of the Mindfulness-Based Stress Reduction program (including practices such as awareness of breath, awareness of body sensations ("body scan"), awareness of sounds, emotions, and thoughts, open awareness, as well as cultivating mindfulness throughout daily activities). Participants will be asked to practice the mindfulness exercises for 15 minutes a day using audio recordings developed by our group. Our team has successfully delivered this intervention in a sample of pregnant women at risk for preterm delivery.

Phase 2: Quantitative Evaluation of Feasibility and Acceptability. Measures of feasibility will include recruitment and retention rates, as well as adherence to the intervention. Specifically, we will measure the number of participants screened and eligible to participate, the number and reasons for refusal, the number and reason for dropout, and the number lost to follow-up. We will also measure the number of MT sessions attended and the minutes spent listening to the guided mindfulness practice recordings. The study will be considered feasible if > 75% of participants complete ≥ 4 sessions and practice mindfulness exercises for 15 minutes a day for ≥ 4 days a week. Acceptability will be measured using the Client satisfaction Questionnaire (CSQ-8 (Larsen, Attkisson et al. 1979)). Scores on the CTQ-8 range from 8-32. The study will be considered acceptable if > 75% of participants report a score of ≥ 20 .

SUSPENDED DURING COVID19 PANDEMIC. **Secondary Outcome Measurement.** Blood pressure will be assessed using *ambulatory blood pressure monitoring* (ABPM, ScottCare device). This validated device (Zawadzki, Vandekar et al. 2013) can measure BP every 30 minutes for 24 hours. ScottCare

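### The claim of sufficient power for feasibility and acceptability has no support for the 75% rules, which in a 15-woman arm mean at least 12 of 15 and say little when the true rate is between about 66% and 84%

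*Combined protocol and SAP*

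**What the plan says.** Specific Aim 1 sets the primary endpoints: "Primary outcomes are feasibility and acceptability". It assigns 15 women to mindfulness training (MT) and 15 to treatment as usual. It describes feasibility by session attendance alone (more than 75% attending at least 4) and acceptability as a satisfaction score above 20, with no proportion clearly attached to the score.

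Phase 2 (Quantitative Evaluation of Feasibility and Acceptability) gives the fuller rules. On feasibility: "The study will be considered feasible if > 75% of participants complete ≥ 4 sessions and practice mindfulness exercises for 15 minutes a day", on at least 4 days a week. On acceptability: "The study will be considered acceptable if > 75% of participants report a score of ≥ 20". Neither rule gives a denominator as a number, a required count or a confidence interval.

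Under Statistical Approach, Sample size considerations, the plan states: "The proposed sample size was estimated to have sufficient power to assess feasibility and acceptability". The same sentence promises confidence intervals, but for secondary outcomes. The paragraph continues: "We propose to enroll 30 participants in a 1:1 ratio to mindfulness training and usual care". Its only numerical support is: "With a two-sided alpha-level of 0.05, we will have more than sufficient power (>80%) to detect acceptability differences" of d = 0.45 or w = 0.2. The one disclaimer about power, in Aim 1, concerns blood pressure: "We will explore preliminary effects (not powered for efficacy) of group differences in ambulatory blood pressure".

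**The concern.** The power claim covers the primary outcomes, but the figure beneath it is for a different quantity. A between-group difference in acceptability does not show how well one arm's observed proportion can be judged against 75%. For that, the plan would need an unacceptable rate and a target rate, or at least the precision expected with the women available. It gives neither.

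The results are meant to inform a fully powered trial. If the sufficient-power statement is taken at face value, a bare pass could be read as firm evidence that more than three quarters of such women will adhere. A bare fail could be read as firm evidence that they will not. Fifteen women support neither reading.

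**Working it through.** **Inputs.** From the plan: 15 women in MT (Specific Aim 1); rule of more than 75% (Phase 2); N = 30 at 1:1, two-sided alpha 0.05, power above 80%, d = 0.45 / w = 0.2 (Sample size considerations). True rates from 60% to 90% are illustrative assumptions, because the plan gives none. For feasibility, the true rate is the share of women who meet the whole criterion, sessions and practice together.

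**1. The plan's own power figure.**
- d = 0.45, 15 per arm: noncentrality = 0.45 × √(15/2) = 1.23. Two-sided two-sample t power = 0.22.
- w = 0.2, N = 30, 1 df: noncentrality = 30 × 0.2² = 1.2. Chi-square power = 0.19.
- For 80% power, d = 0.45 needs about 79 per arm, and w = 0.2 needs (1.960 + 0.842)² / 0.04 ≈ 197 in total.

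The stated figure of more than 80% does not reproduce. Even if it did, it would not bear on a one-arm proportion.

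**2. The count that the rule requires.** 11/15 = 73.3% fails and 12/15 = 80.0% passes, so the operative bar is 80%.

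**3. Probability of passing.** P(X ≥ 12), X ~ Binomial(15, p):

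| True rate p | P(pass) |
|---|---|
| 60% | 0.09 |
| 70% | 0.30 |
| 75% | 0.46 |
| 80% | 0.65 |
| 85% | 0.82 |
| 90% | 0.94 |

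At p = 75% the sum is 0.225 + 0.156 + 0.067 + 0.013 = 0.461. Solving P(pass) = 0.20 and 0.80 gives p = 66% and 84%. Between these rates, about 18 points apart, neither verdict is dependable. A true 80%, above the plan's threshold, fails with probability 1 − 0.65 = 0.35; a true 70%, below it, passes with probability 0.30.

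**4. Precision of a passing result** (Clopper-Pearson 95% limits):

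| Result | Exact 95% CI |
|---|---|
| 12/15 | 52% to 96% |
| 13/15 | 60% to 98% |
| 14/15 | 68% to 99.8% |
| 15/15 | 78% to 100% |

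Only 15/15 has an interval that lies wholly above 75%.

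**5. Sensitivity to the denominator.** If only women who return the CSQ-8 are counted, the cut moves. With 13 women it is 10 (P(pass) = 0.58 at a true 75%); with 12 women it is also 10 (0.39). If the CSQ-8 were scored in all 30 women, the cut would be 23 (22/30 = 73.3%), with P(pass) = 0.28, 0.51 and 0.76 at true rates of 70%, 75% and 80%.

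**The case against.** Several objections have force.

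First, a reader might infer from the 0.46 at a true 75% that the verdict is a coin toss and that the design has no ability to assess feasibility. That does not follow. Any rule based on an observed proportion is near 50:50 when the truth sits at its cut-off; with 30 women the figure is still 0.51. What matters is the width of the grey zone. Outside it the rule does reasonably well for a pilot: it passes 9% of the time at a true 60% and 94% at a true 90%.

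Second, a reader might treat 75% as a null hypothesis and fault the design for lacking power to reject it. The plan states no such test. Phase 2 sets a descriptive benchmark and does not say that a pass would prove a population rate above 75%.

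Third, nothing in the documents makes 12/15 the sole gate to a larger trial. Recruitment, refusal, dropout, retention and the qualitative interviews are also to be used.

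Fourth, the denominator of 15 is firm for sessions and practice but inferred for the CSQ-8. Follow-up satisfaction is not expressly limited to the MT arm, and the sample-size text speaks of a difference in acceptability.

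All four stand, and they limit the point. They do not rescue the power claim. That a pilot need not be powered is no defence either, because this plan says that it is, for these outcomes, and its disclaimer covers only the blood-pressure comparisons.

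**Conclusion.** The plan claims a property for its primary outcomes that it does not support. No calculation addresses the 75% rules, and the one figure given concerns another quantity and is about 19–22% where more than 80% is stated. With 15 women each rule means at least 12, gives an undependable verdict for true rates from about 66% to 84%, and can be met by a result whose exact interval reaches down to 52%.

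The conclusion is limited to that. The documents do not support saying that the rules are worthless or that the sample is unfit for a pilot.

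The figures assume independent women, all 15 MT women counted, and the CSQ-8 rating the MT program. They also depend on which definition applies. Aim 1 counts sessions only and asks for a score above 20; Phase 2 adds practice and accepts a score of 20. These must be reconciled before any pass probability is final.

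**What to change.** 1. First reconcile Specific Aim 1 with Phase 2: whether feasibility includes the practice condition, whether a CSQ-8 score of exactly 20 counts, and whether the 75% proportion applies to the score.
2. State each rule as at least 12 of all 15 women randomized to MT, in line with the intent-to-treat statement under Missing data, and say how a woman with no CSQ-8 or no practice record is counted. State that the CSQ-8 rule applies to the MT arm, if that is the intention.
3. Replace the sufficient-power claim, and the d = 0.45 / w = 0.2 figure offered for it, with what the design delivers. For example: with 15 women in the MT arm, the rule is met with probability 0.09, 0.30, 0.46, 0.65, 0.82 and 0.94 at true rates of 60, 70, 75, 80, 85 and 90%; the lowest passing result, 12/15, has an exact 95% CI of 52% to 96%.
4. Report each primary proportion with its exact 95% CI, and describe a pass as meeting a pilot benchmark, not as evidence that the true rate exceeds 75%.

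The cost is wording only: no added participants and no change in conduct. The stated property becomes less favourable.

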software automatically scores blood pressure readings to calculate average daytime, nighttime, and diurnal systolic, and diastolic blood pressure, hyperbaric index, blood pressure variability, and dipping status (BP fall > 10% from daytime levels). Prior research demonstrates high sensitivity and specificity of ABPM (specifically the hyperbaric index, an index of BP load on organs, blood pressure variability, and dipping status) in the early detection of hypertension. Peripheral blood will be collected via venipuncture before and after the 8-week mindfulness or treatment as usual interval. Samples will be de-identified and stored for future research purposes. (Participants will consent to the collection and banking of blood using a separate consent form.) Research ultrasonography assessments will also be performed before and after the 8-week mindfulness intervention or treatment as usual. The collection of maternal and fetal ultrasound findings will allow evaluation of maternal uterine artery Doppler parameters, placenta size, fetal growth velocity rate and fetal Doppler parameters among the two study groups. Diagnoses of hypertensive disorders will be collected via medical chart review and rates of recurrence will be compared across groups. We will conduct linear mixed effects models to evaluate changes in blood pressure (dependent variable) according to time, group, and time x group interaction (independent variables).

Phase 3: Qualitative Evaluation of Feasibility and Acceptability. Following the intervention, women will be asked to complete in-depth qualitative interviews to solicit feedback on the intervention. Feedback from qualitative interviews will be used to identify patterns and themes in participants' responses that will then be used to further tailor and refine the phone-delivered MT intervention for pregnant women with histories of hypertensive disorders of pregnancy in preparation for a future fully-powered RCT.

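### The nocturnal blood pressure fall is listed only as a yes/no dipping status with no stated method; analysing it as a continuous percentage would gain precision at no data cost

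*Combined protocol and SAP*

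**What the plan says.** All references are to the combined protocol and SAP.

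- **Measure.** The Secondary Outcome Measurement paragraph (Phase 2) and the Ambulatory Blood Pressure Monitoring paragraph (Procedures) say the device software will "calculate average daytime, nighttime, and diurnal systolic, and diastolic blood pressure, hyperbaric index, blood pressure variability, and dipping status". Dipping is defined as "dipping status (BP fall > 10% from daytime levels". Neither place lists a percentage fall or a night-to-day ratio, or says whether the fall is systolic, diastolic or both.
- **Role.** Specific Aim 1 states: "We will explore preliminary effects (not powered for efficacy) of group differences in ambulatory blood pressure". Its list of those measures ends with dipping status, so dipping is an outcome to be compared between arms as well as a software output.
- **Model.** Secondary Outcome Measurement states: "We will conduct linear mixed effects models to evaluate changes in blood pressure (dependent variable) according to time, group, and time x group interaction". No logistic, exact or other method for a yes/no measure appears anywhere.
- **Purpose of the sample.** Sample size considerations states: "We propose to enroll 30 participants in a 1:1 ratio to mindfulness training and usual care". Part of the justification is to "provide a reasonable sample with which to estimate effect sizes and confidence intervals for secondary outcomes".
- **Status.** Ambulatory monitoring is marked as suspended during the COVID-19 pandemic.

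**The concern.** The nocturnal fall is by nature a continuous quantity. Cutting it at 10% treats falls of 9.9% and 10.1% as opposite results and treats all falls on the same side of the cut as equal. In a 30-woman pilot whose secondary outcomes are meant to yield effect sizes and confidence intervals, that widens an interval that will be wide anyway.

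The plan also leaves the analyst without a method. The one named model is built for a continuous response, and nothing says how dipping status will be compared or summarised. The continuous version fits that model directly and needs only numbers the software already delivers.

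**Working it through.** **Plan's own figure.** There is none for dipping status or any other blood pressure outcome. The only power statement concerns acceptability and is not used here.

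**Inputs from the documents.** 30 women randomised 1:1, so 15 per arm; dipping cut at a fall above 10%; day and night means available for systolic and diastolic pressure.

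**Assumptions, not in the documents.** The percentage fall is roughly normal with equal SD in both arms; the dipper rate p is 30% to 70% (20% or 80% shown as a further range); there is one between-arm comparison at follow-up, with complete data.

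**Step 1: information kept.** For a small shift in a normal variable cut at a point that leaves a proportion p on one side, the efficiency of the yes/no comparison relative to the continuous one is

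RE = φ(z_p)² / [p(1 − p)],

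where φ is the standard normal density and z_p the normal quantile of p. Interval width scales as 1/√RE.

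| Dipper rate | RE | 1/√RE | Interval wider by |
|---|---|---|---|
| 50% | 0.3989² / 0.25 = 0.637 | 1.253 | 25% |
| 30% or 70% | 0.3477² / 0.21 = 0.576 | 1.318 | 32% |
| 20% or 80% | 0.490 | 1.429 | 43% |

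Across dipper rates of 30% to 70%, the loss is therefore about 36% to 42% of the information. Put as numbers of women, 30 analysed as yes/no carry about what 0.637 × 30 = 19 (50% dippers) or 0.576 × 30 = 17 (30% or 70%) would carry if analysed continuously.

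**Step 2: absolute size.** With 15 per arm, the half-width of the 95% interval for the difference in mean fall is about 1.96 × √(2/15) = 0.72 SD. Recovered from dipping status, the same shift has a half-width of 0.716 × 1.253 = 0.90 SD at 50% dippers, or 0.716 × 1.318 = 0.94 SD at 30% or 70%. On the reported scale at 50% dippers, the interval for the difference in dipper rates is ±1.96 × √(2 × 0.5 × 0.5/15) = ±36 percentage points.

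**Step 3: limits.** The ratio in step 1 does not depend on the number of women, but the widths in step 2 do and would grow if fewer women have ambulatory data. The planned model uses two visits; the ratio was not worked out for that design.

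**The case against.** Several points on the other side stand.

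- **These outcomes are exploratory.** Specific Aim 1 says they are not powered for efficacy, so no power claim is harmed. Precision is the right yardstick.
- **The raw information is kept.** Day and night means are outcomes in their own right. Subtracting the two treatment estimates gives a point estimate for the absolute day-night difference. It gives neither the percentage fall nor a confidence interval, which needs the within-woman covariance of day and night values.
- **Dipping status has a rationale.** Secondary Outcome Measurement cites its value in early detection of hypertension. That supports reporting it, but not reporting it alone.
- **The list is already long**, and the proposal adds two derived outcomes.

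A reader might go further in three ways that the documents do not support.

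1. *The plan fits a linear model to a yes/no outcome.* The model's dependent variable is blood pressure, and nothing assigns dipping status to it. The method is missing; there is no stated error. For the same reason, the fragility of a binary mixed model in this sample cannot be charged to the plan, which does not propose one.
2. *The trial loses the blood pressure signal it seeks.* Anticipated Outcomes refers to change in maternal blood pressure and does not name dipping. The continuous means carry that signal.
3. *Power collapses from 56% to 22%.* Those figures assume a 0.8 SD shift, which is nowhere in the documents, with 50% dippers in usual care. Half of the drop comes from the choice of Fisher's exact test: uncorrected chi-square gives 39%, so 56 − 39 = 17 points come from the cut and 39 − 22 = 17 from the test. At 0.45 SD, a value the plan gives only for acceptability, the figures are 22% (t-test) against 14% to 16% (chi-square or normal approximation at dipper rates of 30% to 70%). Both are weak.

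**Conclusion.** The point holds as a cheap improvement. The nocturnal fall is an exploratory between-arm outcome listed only in dichotomised form, with no method stated, while a continuous version that fits the planned model is already within reach. The cost of the yes/no form is about 36% to 42% of the information, or intervals about 25% to 32% wider, on this one outcome. That rests on approximate normality and an assumed dipper rate of 30% to 70%; a rate further from 50% makes the loss larger. The primary feasibility and acceptability outcomes and the day and night means are not touched. The change has practical effect only if ambulatory monitoring is collected.

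**What to change.** In Secondary Outcome Measurement:

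- Add percentage nocturnal fall, (day mean − night mean)/day mean, for systolic and for diastolic pressure, as continuous outcomes in the planned linear mixed model with time, group and time-by-group terms. Report effect estimates with 95% confidence intervals.
- Report dipping status descriptively, as counts by arm and visit, and state which pressure defines it.
- Label both percentage falls as exploratory.

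The cost is a few lines of SAP wording and two more derived exploratory outcomes. No new data, visits or participants are needed.
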